11.2.3. Demography

Age: Age at the reference activity, computed as the number of units between the date of birth and the reference activity.

Conversion of weight to kg

The following conversion rule is used:

Weight in Kilogram= weight in Pounds / 2.2

Weight in Kilogram =weight in oncs / 35.2

The result is rounded to 2 decimals.

Conversion of height to cm

The following conversion rule is used:

Height in Centimetres = Height in Feet * 30.48

Height in Centimetres = Height in Inch * 2.54

The result is rounded to the unit (i.e no decimal)

Conversion of temperature to °C

The following conversion rule is used:

Temperature in °Celsius = ((Temperature in °Fahrenheit -32) *5)/9

The result is rounded to 1 decimal.

11.2.4. Immunogenicity

For a given subject and given immunogenicity measurement, missing or non-evaluable measurements will not be replaced. Therefore, an analysis will exclude subjects with missing or non-evaluable measurements.

The Geometric Mean Concentrations/Titres (GMC/Ts) calculations are performed by taking the anti-log of the mean of the log titre transformations. Antibody titres below the cut-off of the assay will be given an arbitrary value of half the cut-off of the assay for the purpose of GMT calculation. The cut-off value is defined by the laboratory before the analysis and is described in the protocol.

A seronegative subject is a subject whose antibody titre is below the cut-off value of the assay. A seropositive subject is a subject whose antibody titre is greater than or equal to the cut-off value of the assay.

The assay cut-off is the value under which there is no quantifiable result available. For an assay with a specific 'cut_off', numerical immunogenicity result is derived from a character field (rawres):

If rawres is 'NEG' or '-' or '(-)', numeric result= cutt_off/2,

if rawres is 'POS' or '+' or '(+)', numeric result = cut_off,

if rawres is '< value' and value<=cut_off, numeric result =cut_off/2,

if rawres is '< value' and value>cut_off, numeric result =value,

if rawres is '> value' and value<cut_off, numeric result =cut_off/2,

if rawres is '> value' and value>=cut_off, numeric result =value,

if rawres is '<= value' or '>= value' and value<cut_off, numeric result =cut_off/2,

if rawres is '<= value' or '>= value' and value>=cut_off, numeric result =value,

if rawres is a value < cut_off, numeric result = cut_off/2,

if rawres is a value >= cut_off, numeric result = rawres,

if rawres is a value >= cut_off, numeric result = rawres,

else numeric result is left blank.

All CI computed will be two-sided 95% CI.

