1. INTRODUCTION

1.1. Background

Infants experience the highest rates of serious complications, hospitalisations and death due to pertussis. This is mainly because they are too young to have completed the primary diphtheria, tetanus and acellular pertussis (DTPa) immunisation series.

Since 2000, most deaths and hospitalisations related to pertussis have been in unvaccinated infants younger than three months of age [Murphy, 2008]. In 2012, there were 48,777 reported cases of pertussis in the United States (US). Infants younger than one year of age had the highest incidence compared to other studied age groups. Fifteen out of 20 deaths occurred in unvaccinated infants younger than three months of age. In 2013, there were 24,231 reported cases of pertussis in the US. The incidence again was highest in infants younger than one year of age and all of nine deaths due to pertussis occurred in unvaccinated infants three months of age and younger [CDC, 2013a; CDC, 2013b].

In Canada, approximately 2500 cases were reported in 2012 [Public Health Agency of Canada, 2012]. The United Kingdom was amidst a large outbreak of pertussis in 2012. A national increase in the laboratory-confirmed cases of pertussis has also been observed in England and Wales, with a large number of cases being reported in very young infants [Health Protection Report, 2012]. The number of pertussis cases reported in Australia has also been increasing with nearly 40,000 cases reported in 2011 and 2012. While the rates are highest in the primary school-aged children, due to the waning of vaccine-induced immunity, the impact of the disease remains greatest in infants under one year of age [Communicable Disease Control Directorate, 2011].

Transplacental transfer of maternal antibodies is considered to provide some degree of protection to infants in the first few months of their life. Unfortunately, low levels of the maternal antibodies and rapid decay of the antibodies in the infants often leave them at high risk for pertussis. One way to confer protection to infants is to immunise mothers late during pregnancy. This concept of “boosting” maternal levels of antibody to pertussis has been suggested as early as 1995. However, the findings that pre-existing high levels of pertussis antibody in infants suppress the ultimate immune response to whole-cell diphtheria, tetanus and pertussis (DTP) vaccines lessened the enthusiasm for this approach [Englund, 1995].

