10.3. Determination of sample size

The sample size for this study is not derived from any power based calculation. The sample size would consist of all infants whose mothers were enrolled in the study 116945 [DTPA (BOOSTRIX)-047]. Considering approximately 10%-30% reduction in the number of evaluable subjects due to drop-outs and protocol violations from the initial

study, the table below gives the estimated sample size of evaluable subjects that can be expected and the precision achieved with this sample for various expected values.

Table 22 Exact 95% CI of the different values of observed response rate (vaccine response rate or seroprotection rate) for a sample size of 238-300 subjects)

Number of evaluable subjects	Observed response rate expressed as a percentage	Exact 2-sided 95% CI for this observed rate for a sample size of 300 subjects	
		Lower Limit (LL)	Upper Limit (UL)
300	70	64.5	75.1
	75	69.7	79.8
	80	75.0	84.4
	85	80.4	88.8
	92	88.3	94.8
	93	89.5	95.6
	94	90.7	96.4
	95	91.9	97.2
	96	93.1	97.9
	97	94.4	98.6
	98	95.7	99.3
	99	97.1	99.8
272	70	64.4	75.6
	75	69.4	80.0
	80	74.9	84.7
	85	80.5	89.3
	92	88.4	95.2
	93	89.3	95.7
	94	90.6	96.6
	95	92.0	97.4
	96	92.9	98.0
	97	94.3	98.7
	98	95.8	99.4
	99	97.4	99.9
238	70	63.9	75.9
	75	69.2	80.6
	80	74.6	85.1
	85	80.1	89.5
	92	87.8	95.1
	93	89.3	96.1
	94	90.3	96.7
	95	91.4	97.4
	96	92.9	98.3
	97	94.0	98.8
	98	95.8	99.5
	99	97.0	99.9
	100	98.5	100.0

Reference study:

217744/070: Group receiving DTPa-HBV-IPV/Hib full-term infants according to 2, 4, 6 schedule in Spain.

217744/078: Group receiving DTPa-HBV-IPV/Hib +Prevenar according to 2, 3, 4 schedule in Germany.

217744/054: Group receiving DTPa-HBV-IPV/Hib according to 3,5,11 schedule in Italy and Germany [Hardy-Fairbanks, 2013]. Based on this reference, the confidence interval of lower response rate also included in case of any immune interference.

The reference values are presented in [Table 23](#).

CONFIDENTIAL

201330 [DTPA (BOOSTRIX)-048 PRI]
Protocol Amendment 1 Final

Table 23 Reference values

Study Group	Schedule (months)	N	D	T	PT VR	FHA VR	PRN VR	HBs	POLIO TYPE 1	POLIO TYPE 2	POLIO TYPE 3	PRP
217744/070												
DTPa-HBV-IPV/Hib pre-term	2,4,6	93	100	100	98.9	100	100	93.4	100	100	100	92.5
DTPa-HBV-IPV/Hib full-term	2,4,6	89	100	100	98.9	100	98.9	95.2	100	100	100	97.8
217744/078												
DTPa-HBV-IPV/Hib	2,3,4	138	100	100	100	97.8	97.8	97.8	100	98.4	99.2	95.7

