10.5. Derived and transformed data

The cut-off value is defined by the laboratory before the analysis and is described in the laboratory assays section (Section 5.7.1).

- A seronegative subject is a subject whose antibody concentration/titre is below the assay cut-off.
- A seropositive subject is a subject whose antibody concentration/titre is greater than or equal to the assay cut-off defined in [Table 11](#).
- A seroprotected subject is a subject whose antibody concentration/titre is greater than or equal to the level defining clinical protection. The following seroprotection thresholds are applicable:
 - Anti-diphtheria antibody concentrations ≥ 0.1 IU/ml.
 - Anti-tetanus antibody concentrations ≥ 0.1 IU/ml.
 - Anti-HBs antibody concentrations ≥ 10 mIU/mL.
 - Anti-poliovirus types 1, 2 and 3 antibody titres ≥ 8 .
 - Anti-PRP antibody concentrations ≥ 0.15 μ g/ml.
- Other cut-offs to be considered:
 - Anti-PRP antibody concentrations ≥ 1.0 μ g/ml.
 - Anti-diphtheria antibody concentrations ≥ 1.0 IU/ml.
 - Anti-tetanus antibody concentrations ≥ 1.0 IU/ml.
 - Anti-HBs antibody concentrations ≥ 100 mIU/mL.
- For the pneumococcal antigens, the threshold used for statistical analysis will depend on the final selected assay.
- Vaccine response to the PT, FHA and PRN antigens, is defined as:
 - appearance of antibodies in subjects who were initially seronegative (i.e., with concentrations <cut-off value).
 - at least maintenance of pre-vaccination antibody concentrations in subjects who were initially seropositive (i.e., with concentrations \geq cut-off value).
- The geometric mean titres (GMTs)/geometric mean concentrations (GMCs) calculations will be performed by taking the anti-log of the mean of the \log_{10} titre/concentration transformations. Antibody titres/concentrations below the cut-off

of the assay will be given an arbitrary value of half the cut-off for the purpose of GMT/GMC calculation.

Handling of missing data:

Immunogenicity

For a given subject and a given immunogenicity measurement, missing or non-evaluable measurements will not be replaced. Therefore, an analysis will exclude subjects with missing or non-evaluable measurements.

Safety/reactogenicity

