4.2. Secondary endpoints

- Persistence of antibodies before the first dose of *Infanrix hexa*.
 - Anti-diphtheria and anti-tetanus seroprotection status, anti-PT, anti-FHA, anti-PRN seropositivity status and antibody concentrations.
- Immunogenicity with respect to components of *Infanrix hexa* and Prevenar 13.
 - Anti-diphtheria, anti-tetanus, anti-poliovirus type 1, anti-poliovirus type 2, anti-poliovirus type 3, anti-HBs, anti-PRP, anti-PT, anti-FHA, anti-PRN and anti-pneumococcal serotypes (1, 3, 4, 5, 6A, 6B, 7F, 9V, 14, 18C, 19A, 19F, 23F) antibody concentrations or titres, one month after the last dose of primary vaccination.
- Immunogenicity with respect to components of *Infanrix hexa*.
 - Anti-PT, anti-FHA, anti-PRN antibody seropositivity status, one month after the last dose of primary vaccination.

- Solicited local and general symptoms.
 - Occurrence of solicited local/general symptoms during the 4-day (Day 0-Day 3) follow-up period after each vaccination.
- Unsolicited adverse events.
 - Occurrence of unsolicited symptoms during the 31-day (Day 0-Day 30) follow-up period after each vaccination.
- Serious adverse events.
 - Occurrence of SAEs from first vaccination dose to study end.

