11. ANNEX 1 STANDARD DATA DERIVATION RULE AND STATISTICAL METHODS

11.1. Statistical Method References

- The exact two-sided 95% CIs for a proportion within a group will be the Clopper-Pearson exact CI [Clopper CJ, Pearson ES. The use of confidence or fiducial limits illustrated in the case of binomial. *Biometrika*. 1934; 26:404-413].
- The 95% CI for geometric mean titers/concentrations (GMTs/GMCs) will be obtained within each group separately. The 95% CI for the mean of log-transformed titer/concentration will be first obtained assuming that log-transformed values were normally distributed with unknown variance. The 95% CI for the GMTs/GMCs will be then obtained by exponential-transformation of the 95% CI for the mean of log-transformed titer/concentration.

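### With heavy censoring at the assay cut-off, plausible but not quantified for Control pertussis antigens at Pre-Pri, half-cut-off substitution biases the GMC and its 95% CI can fall well below nominal coverage

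*SAP*

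**What the plan says.** The SAP fixes the GMC interval in two places. In 11.1, the interval for the mean log concentration "will be first obtained assuming that log-transformed values were normally distributed with unknown variance", separately in each group, and is then back-transformed. In 11.2.4: "Antibody titres below the cut-off of the assay will be given an arbitrary value of half the cut-off of the assay". Protocol 10.5 has the same rule: a value below the cut-off "of the assay will be given an arbitrary value of half the cut-off for the purpose of GMT/GMC calculation". SAP 11.2.4 describes the cut-off as the limit under which the assay gives no quantifiable result, so these values are left-censored by the SAP's own definition. It also sets the level: "All CI computed will be two-sided 95% CI".

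Template 10 calculates GMCs on all subjects, so substituted values enter both the mean and the SD. It prints them at Pre-Pri and Post-Pri for both groups. Pre-Pri pertussis results are a pre-specified secondary endpoint (SAP 4.2): "anti-PT, anti-FHA, anti-PRN seropositivity status and antibody concentrations". No censored-data method or sensitivity analysis is planned.

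**The concern.** Replacing a whole lower tail by one value changes both the mean and the spread of the log concentrations. The interval in SAP 11.1 takes no account of this, and the bias does not shrink as the sample grows.

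The persistence endpoint is where it could matter. Protocol 1.1 describes unboosted maternal pertussis antibody in terms of "low levels of the maternal antibodies and rapid decay of the antibodies in the infants". Protocol 1.2.1 reports high pertussis antibody in infants whose mothers were vaccinated in pregnancy. Substitution could therefore be common in Control and rare in dTpa, so that the two Pre-Pri GMCs, printed one below the other, carry different biases. Because the study is descriptive, the estimate and its interval are the whole result.

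**Working it through.** **Inputs.**
- Interval: t-interval on log10 values (SAP 11.1), two-sided 95% (SAP 11.2.4).
- Substitution: half the cut-off, which is log10(2) = 0.301 below it. The cut-off itself drops out of the bias.
- Sample size: n = 240 per group, near the lower end of Protocol Table 22, drawn up "for a sample size of 238-300 subjects".
- Share below the cut-off, f: not in the documents; assumed 20% to 70%.
- SD of log10 concentration, σ: not in the documents; assumed 0.35 to 0.65.

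**Step 1: the plan's own level.** With exactly log-normal data and nothing below the cut-off, simulated coverage is 94.9% (n = 238), 95.2% (n = 272) and 95.0% (n = 300). The stated 95% reproduces.

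**Step 2: closed form with substitution.** Let z = Φ⁻¹(f), with φ(z) the normal density at z, and let Y be the substituted log10 value measured from the cut-off.
- Bias: b = σ[f·z + φ(z)] − 0.301·f. The GMC is multiplied by 10^b.
- Mean: E(Y) = −0.301·f + σ[φ(z) − z(1 − f)].
- Second moment: E(Y²) = f·0.301² + σ²[(1 + z²)(1 − f) − z·φ(z)].
- SE = √[(E(Y²) − E(Y)²)/n].
- Coverage ≈ Φ(1.96 − b/SE) − Φ(−1.96 − b/SE).

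Example, σ = 0.5, f = 50%, n = 240 (z = 0, φ = 0.399):
- b = 0.5 × 0.399 − 0.301 × 0.5 = 0.1995 − 0.1505 = 0.049, so the GMC is 10^0.049 = 1.12 times the truth.
- E(Y) = 0.049 and E(Y²) = 0.5 × 0.0906 + 0.25 × 0.5 = 0.170, giving SD 0.410 and SE = 0.410/√240 = 0.0265.
- b/SE = 1.85; coverage ≈ Φ(0.11) = 54%. Simulation gives 56%.

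**Step 3: simulation, n = 240, 10,000 runs per cell.** Coverage of the true GMC, with the GMC bias ratio in brackets:

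| Below cut-off | SD 0.35 | SD 0.40 | SD 0.45 | SD 0.50 | SD 0.65 |
|---|---|---|---|---|---|
| 20% | 87% (0.95) | 91% (0.96) | 93% (0.98) | 94% (0.99) | 94% (1.03) |
| 30% | 83% (0.95) | 92% (0.97) | 95% (0.99) | 95% (1.01) | 86% (1.08) |
| 40% | 84% (0.95) | 94% (0.99) | 94% (1.02) | 89% (1.05) | 55% (1.16) |
| 50% | 92% (0.98) | 94% (1.02) | 80% (1.07) | 56% (1.12) | 6% (1.28) |
| 60% | 94% (1.02) | 63% (1.08) | 19% (1.15) | 3% (1.23) | 0% (1.48) |
| 70% | 34% (1.10) | 1% (1.19) | 0% (1.29) | 0% (1.40) | 0% (1.79) |

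Larger groups do worse: at SD 0.5 with 50% below, coverage is about 50% at n = 272 and 46% at n = 300. Outside the table, at SD 0.3 and n = 272, coverage is already 61% with 30% below, and the GMC is 7% too low.

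**Step 4: a left-censored log-normal likelihood.** With a Wald 95% interval and log-normality true, coverage was 91% to 96% over SD 0.35 to 0.65 and 30% to 70% below (500 runs per cell), including cells where the planned interval is near 0%.

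**Step 5: where it should not matter.** The reference rates at or above threshold in Protocol Table 23 run from 92.5% to 100%. Each threshold is at or above the current assay cut-off, and a pertussis vaccine responder is by definition at or above the cut-off afterwards. At most about 7.5% would then be substituted at Post-Pri. With 10% below, the closed form gives 91% to 95% coverage. Table 23 does not cover the pneumococcal serotypes. The primary endpoints are rates and use no GMC.

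**The case against.** **The premise is not quantified.** A reader might infer that most Control infants will be below the cut-off at Pre-Pri. The documents do not support that. Protocol 1.1 is qualitative, and low is not the same as unquantifiable. The seronegative row in Template 13 is no evidence: it appears for both groups, and SAP section 12 says the templates were copied from other studies. SAP section 9 reports lower cut-offs for the re-validated assays, which points to fewer substituted values. This objection stands.

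**The failure is not general.** A reader might also infer that the interval usually misses, or that the benefit of vaccination in pregnancy is always understated. Neither follows. Coverage is 92% to 94% with half below at SD 0.35 to 0.40, and the bias changes sign. This stands too.

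**The target is a choice.** Both documents openly define the GMC with an arbitrary value. For the mean of that defined quantity, coverage is 94% to 96% throughout. That is true, but the table is labelled as a geometric mean concentration and will be read as one.

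**The reader can see the censoring.** Template 10 prints the percentage at or above the cut-off beside each GMC, and Template 14 plots reverse cumulative curves. No between-group GMC ratio or test is planned. This reduces the harm but does not correct the estimate or its interval.

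**The alternative is fragile.** The likelihood fit extrapolates an unseen tail. When an assumed minority of high-antibody infants breaks log-normality, its coverage ranged from 48% to 96%, and in some cells with 50% below the planned interval did better. With 70% below, the planned interval covered 0% to 11%. This is why the fit belongs beside the planned GMC and should not replace it.

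**Conclusion.** The concern holds conditionally. If a large share of a group is below the cut-off, the half-cut-off GMC is biased and its 95% CI can be far from nominal. At n of about 240:
- 50% below: coverage 80% down to about 6% at SD 0.45 to 0.65, but 92% to 94% at SD 0.35 to 0.40.
- 70% below: about 0% at SD 0.40 or more, 34% at SD 0.35.
- 30% below: 83% to 95%.

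The GMC is up to about 5% too low at SD 0.35 with 20% to 30% below, and 7% to 28% too high with 50% below at SD 0.45 to 0.65. Only an upward bias in Control would understate the gap between groups: if the dTpa GMC is unbiased, that 7% to 28% shrinks the visible ratio by 1 − 1/1.07 = 7% to 1 − 1/1.28 = 22%.

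All of this rests on assumed shares and SDs and on log-normal data. It concerns a descriptive secondary endpoint. It does not show that the Pre-Pri intervals will fail, and it does not touch the primary seroprotection and vaccine-response rates. It is a cheap improvement.

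**What to change.** Keep the half-cut-off GMC as planned. Add one paragraph to SAP 11.1 and 11.2.4: for any antigen, group and timepoint with about 40% or more of values below the assay cut-off, also report, as a sensitivity analysis, a GMC and 95% CI from a log-normal likelihood left-censored at the cut-off. Show the share below the cut-off in the same row, and caution against relying on the half-cut-off interval where the two differ.

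The 40% trigger is a judgement: over SD 0.35 to 0.65, it is about where severe loss of coverage can begin. At a smaller SD, losses start at lower shares, so the observed spread should be looked at as well.

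The cost is one standard procedure call, two GMCs in a few rows, and a sensitivity result that itself depends on log-normality in the unobserved tail. If few values are below the cut-off, nothing changes.

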4. ENDPOINTS

4.1. Primary endpoints

- Immunogenicity with respect to components of *Infanrix hexa*.
 - Anti-diphtheria, anti-tetanus, anti-HBs, anti-poliovirus type 1, anti-poliovirus type 2, anti-poliovirus type 3 and anti-polyribosyl-ribitol phosphate (anti-PRP) seroprotection status, one month after the last dose of primary vaccination.

A seroprotected subject is a subject whose antibody concentration/titre is greater than or equal to the level defining clinical protection. The following seroprotection thresholds are applicable:

 - Anti-diphtheria antibody concentrations ≥ 0.1 IU/mL.
 - Anti-tetanus antibody concentrations ≥ 0.1 IU/mL.
 - Anti-HBs antibody concentrations ≥ 10 mIU/mL.
 - Anti-poliovirus types 1, 2 and 3 antibody titres ≥ 8 .
 - Anti-PRP antibody concentrations ≥ 0.15 $\mu\text{g/mL}$.
 - Vaccine response to PT, FHA and PRN antigens, one month after the last dose of primary vaccination.

Vaccine response to the PT, FHA and PRN antigens, is defined as:

- appearance of antibodies in subjects who were initially seronegative (i.e., with concentrations $<$ cut-off value).
- at least maintenance of pre-vaccination antibody concentrations in subjects who were initially seropositive (i.e., with concentrations \geq cut-off value).

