9. CHANGES FROM PLANNED ANALYSES

- During the course of the study, the assays used to measure the anti-D, anti-T, anti-PT, anti-FHA and anti-PRN IgG concentrations were re-developed and re-validated and both assay units and assay cut-offs were adapted. The new ELISA's for PT, FHA and PRN were calibrated against the WHO International Standard (NIBSC 06/140). This allowed the expression of concentrations measured with the new ELISA's in international units per milliliter (IU/mL) instead of the formerly used ELISA units per milliliter (ELU/mL). The newly validated DTPa ELISA's used in the study have a lower assay cut-off as compared to the one described in the protocol. The current assay cut-off is 0.057 IU/mL for anti-D, 0.043 IU/mL for anti-T, 2.693 IU/mL for anti-PT, 2.046 IU/mL for anti-FHA and 2.187 IU/mL for anti-PRN. An agreement between the old and new ELISAs was shown with regards to the two thresholds of clinical relevance for the DI/TE response (0.1 IU/mL and 1.0 IU/mL) and therefore the clinical endpoints and anti-D and anti-T are unchanged. In the absence of a correlate of protection for the B. pertussis antigens, the pertussis endpoints were redefined based on the assay cut-off (see section 5.7.5 of protocol).
- In addition, following CBER feedback on the anti-D re-validated assay, a calibration factor of 0.543 was applied in the analysis of anti-D in order to align the ELISA assay to the WHO 10/262 reference samples which are measured as 2 IU/mL by Di neutralization. Assay since 54 WHO 10/262 reference samples measured by GSK re-validated ELISA led to GMC was about two fold (1.841) higher than the expected value (2 IU/mL).

- Note: Due to re-validation of all assays, the cut-offs presented in Table 11 of the protocol of few antigens have changed. Below table has an updated threshold.

Antigen	Threshold for positivity
• Anti-PT	• 2.693 IU/mL
• Anti-FHA	• 2.046 IU/mL
• Anti-PRN	• 2.187 IU/mL
• Anti-D	• 0.057 IU/mL
• Anti-T	• 0.043 IU/mL
• Anti-polio	• 8 dilution
• Anti-PRP	• 0.066 µg/mL
• Anti-HBs	• 6.2 mIU/mL
• Anti-pneumococcal serotypes (1)	• 0.080 µg/mL
• Anti-pneumococcal serotypes (3)	• 0.075 µg/mL
• Anti-pneumococcal serotypes (4)	• 0.061 µg/mL
• Anti-pneumococcal serotypes (5)	• 0.198 µg/mL
• Anti-pneumococcal serotypes (6A)	• 0.111 µg/mL
• Anti-pneumococcal serotypes (6B)	• 0.102 µg/mL
• Anti-pneumococcal serotypes (7F)	• 0.063 µg/mL
• Anti-pneumococcal serotypes (9V)	• 0.066 µg/mL
• Anti-pneumococcal serotypes (14)	• 0.160 µg/mL

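### SAP 11.2.4 gives unsupported scores to two result types it lists itself: 'POS', and '> value' or '>= value' with a bound below the assay cut-off

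*SAP*

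**What the plan says.** SAP section 11.2.4 derives every numeric immunogenicity result from a character field. For a qualitative positive: "if rawres is 'POS' or '+' or '(+)', numeric result = cut_off". For a result above a bound that lies below the cut-off: "if rawres is '> value' and value<cut_off, numeric result =cut_off/2". The matching line for inclusive bounds puts both directions together: "if rawres is '<= value' or '>= value' and value<cut_off, numeric result =cut_off/2". When the bound reaches the cut-off, the bound itself is used: "if rawres is '> value' and value>=cut_off, numeric result =value".

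The same section gives the definitions that these numbers feed: "A seropositive subject is a subject whose antibody titre is greater than or equal to the cut-off value of the assay", and "The assay cut-off is the value under which there is no quantifiable result available".

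SAP section 9 reports re-validated assays with lower cut-offs: "The current assay cut-off is 0.057 IU/mL for anti-D, 0.043 IU/mL for anti-T". It also lists 0.066 µg/mL for anti-PRP, 6.2 mIU/mL for anti-HBs, 8 for polio, and 2.693, 2.046 and 2.187 IU/mL for anti-PT, anti-FHA and anti-PRN. The seroprotection thresholds in SAP section 4.1 are separate figures, for example "Anti-tetanus antibody concentrations ≥ 0.1 IU/mL"; the others are 0.1 IU/mL for diphtheria, 10 mIU/mL for HBs, 0.15 µg/mL for PRP and 8 for polio. Pertussis vaccine response there requires a concentration at or above the cut-off in infants who start seronegative, and Post-Pri at or above Pre-Pri in those who start seropositive.

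**The concern.** A rule that turns a non-numeric entry into a number should not decide a question that the entry leaves open, and should not contradict the entry. These lines do both. 'POS' says that antibody is present; it does not say whether the level reaches a threshold above the cut-off, yet the rule settles that against the infant. '> value' with a bound below the cut-off does not say on which side of the cut-off the serum lies, yet the rule calls it seronegative, sometimes with a number below the bound that the laboratory reported.

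The derived number is used for the seroprotection rates, the pertussis vaccine responses, the GMCs/GMTs and the reverse cumulative curves. Any wrong number therefore enters the primary endpoints directly. Most reference rates in Protocol Table 23 lie between about 93% and 100%, so even a few forced failures would show.

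**Working it through.** **Method check.** The only precision figures in the plan are the exact intervals in Protocol Table 22. The Clopper-Pearson limits are the 2.5% quantile of Beta(x, n−x+1) and the 97.5% quantile of Beta(x+1, n−x). For 95% of 300, x = 285 gives 91.9 to 97.2, as printed there.

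**'POS' against the seroprotection thresholds.** The assigned value is the cut-off (SAP 9), compared with the threshold (SAP 4.1).

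| Antigen | Cut-off = value for 'POS' | Threshold | Score given to 'POS' |
|---|---|---|---|
| Diphtheria (IU/mL) | 0.057 | 0.1 | seropositive, not seroprotected |
| Tetanus (IU/mL) | 0.043 | 0.1 | seropositive, not seroprotected |
| PRP (µg/mL) | 0.066 | 0.15 | seropositive, not seroprotected |
| HBs (mIU/mL) | 6.2 | 10 | seropositive, not seroprotected |
| Polio 1, 2, 3 (titre) | 8 | 8 | seroprotected |

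Four of the seven seroprotection endpoints are affected. All pneumococcal cut-offs (0.061 to 0.199 µg/mL) are below the 0.35 µg/mL level in SAP 6.3.2, so 'POS' would fail that level too.

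**Bound below the cut-off.** The assigned value is cut-off/2, always below the cut-off and so always seronegative.
- Anti-T '>0.03': 0.03 < 0.043, so the value is 0.043/2 = 0.0215, which is below 0.03.
- Anti-PT '>2.5': 2.5 < 2.693, so the value is 2.693/2 = 1.3465, which is below 2.5.

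The number contradicts the report when the bound lies between cut-off/2 and the cut-off. With a smaller bound it is possible but arbitrary.

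**Pertussis vaccine response, using anti-PT (cut-off 2.693; concentrations are illustrative).**
- Pre 50, Post 20, both numeric: 20 < 50, a non-response.
- Same infant with Pre reported as 'POS': Pre = 2.693 and 20 ≥ 2.693, a response. Any seropositive Post-Pri would qualify.
- Same infant with Pre reported as '>2.5': Pre = 1.3465, classed seronegative; 20 ≥ 2.693, a response.
- Pre 50, Post 'POS': Post = 2.693 < 50, a non-response whatever the true Post-Pri level.

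**Size if such results occur.** The documents give no frequency. Assume that a share of sera are 'POS', that all are truly protected, and that the true rate is 100%.

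| n (Table 22) | 'POS' sera | Scored rate | Exact 95% CI |
|---|---|---|---|
| 300 | 0 | 100% | 98.8 to 100 |
| 300 | 3 | 99.0% | 97.1 to 99.8 |
| 300 | 6 | 98.0% | 95.7 to 99.3 |
| 300 | 15 | 95.0% | 91.9 to 97.2 |
| 238 | 0 | 100% | 98.5 to 100 |
| 238 | 2 | 99.2% | 97.0 to 99.9 |
| 238 | 12 | 95.0% | 91.4 to 97.4 |

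Each serum costs 1/300 = 0.33 points at n = 300.

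For the anti-D GMC, assume a share f of sera are 'POS' with a true level of 1.0 IU/mL. The GMC is multiplied by (0.057/1.0)^f: 0.972 for f = 1% and 0.944 for f = 2%.

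**The case against.** The best defence is that this is a standard annex written for any assay, and that the lines may never be used. Protocol Table 11 lists quantitative methods with numeric units (ELISA, chemiluminescence, neutralisation, multiplex). Neither document says that any of them reports 'POS' or '> value'. All analyses are descriptive, with no test or margin at stake. This stands as a limit on size, not as a defence of the rule: the SAP lists these entries itself and prescribes a score for them.

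It is also fair that a 'POS' serum lying between cut-off and threshold is rightly unprotected. The fault is deciding it without evidence; no particular serum is shown to be misclassified.

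Several stronger readings are tempting, and the documents do not support them.
- That known positives are called seronegative. 'POS' equals the cut-off and so counts as seropositive. Only results with a bound below the cut-off become seronegative, and those are undetermined.
- That lowering the cut-offs reversed an existing rule. With the Protocol Table 11 cut-offs (0.1, 0.1, 0.15), 'POS' would have met the D, T and PRP thresholds. But the protocol contains no 'POS' rule to reverse, and the HBs gap (6.2 against 10) was already there.
- That the lines break the SAP's statement that non-evaluable measurements are not replaced. A reported 'POS' can reasonably be read as a result rather than a non-evaluable one.
- That setting '> value' at or above the cut-off to its bound is equally wrong. It is an ordinary lower-bound value, consistent with the report. It misleads only where the bound does not decide the comparison, as with anti-T '>0.08' against 0.1.

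**Conclusion.** The point holds as a defect in the stated derivation rules. A bound below the cut-off yields a seronegative score for an undetermined serum, and sometimes a number that contradicts the report. 'POS' is automatically unprotected for diphtheria, tetanus, PRP and HBs, and it can decide pertussis vaccine response in either direction.

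The size is unknown and may be zero. The illustrative losses of 1 to 5 percentage points rest on assumed frequencies of about 1% to 5% and on every such serum being truly protected.

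A reader might infer that the error favours one group, because the protocol's rationale describes high infant pertussis antibody after maternal dTpa. That would require 'POS' or right-censored Pre-Pri results to occur, and to occur more often in one group. The documents give no evidence of either.

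**What to change.** Rewrite the 'POS', '> value' and '>= value' lines of SAP 11.2.4.

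- Never assign a number below a stated lower bound. Split the line that treats '<=' and '>=' together; only its '>=' half needs to change.
- Classify against a threshold only when the result decides it: 'POS' is seropositive, and a bound at or above the threshold is seropositive or seroprotected. Otherwise treat the measurement as non-evaluable for that threshold.
- Exclude 'POS' from GMCs, and keep other right-censored values at their bound.
- For pertussis vaccine response, treat every pair with a 'POS' or right-censored Pre-Pri as non-evaluable in the main analysis. Keeping only the pairs that can be decided would admit such infants only as failures: Pre '>30' with Post 20 would count as a non-response, while Pre '>30' with Post 200 would be dropped. Add a sensitivity analysis that counts all these pairs as responses, then all as non-responses. A Post-Pri 'POS' against a numeric Pre-Pri above the cut-off is also undecided and should not be forced to a non-response.
- Footnote the number of such results per antigen and group.

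The cost is SAP wording and a few lines of derivation code. The small downside is that a few measurements may leave some denominators.
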